10.4. Visit 5 Through 10 – Outpatient Stage

10.4.1. Visits 5 Through 10 – Treatment Day 4-113

During the outpatient stage, subjects will return for clinic visits every two weeks. Activities to be performed at these visits are outlined in the Schedule of Activities ([Table 1](#)[bookmark7](#)).

In the outpatient setting, subjects will perform moderate to high intensity aerobic exercise with a target of at least 2-3 qualifying sessions per week. To be eligible for study drug dosing, the planned aerobic exercise will be 30-75 minutes in duration. Additionally, the subject's BGM must range between 100-180 mg/dL (5.56 – 10 mmol/L) before the exercise session. Subjects must record their carbohydrate intake (eg, both dextrose tabs and carbohydrates from food) 15 minutes before exercise, during the exercise session, and up to 5 hours post-exercise session.

During the exercise session, the subject is to only drink carbohydrate free liquids (e.g., Powerade Zero or comparable product) and will be provided with glucose tabs to use as needed. The subject will take 5 BGM measurements with exercise: at -15 minutes and just before exercise to establish baseline value, at 30 minutes into the exercise session, at the end of the exercise session, and at 30 minutes after the exercise session. There is a ± 2 minute window on all of these time points.

Per ADA guidelines, if a subject's glucose falls to ≤ 70 mg/dL (3.89 mmol/L) during any exercise session, then the exercise session should be stopped, and no more exercise should be completed that same day; the subject should rest, and glucose tabs should be taken every 15 minutes until the hypoglycemia is corrected and euglycemia (confirmed by BGM) is maintained. Subjects will be provided with a supply of glucose tabs and instructed to use these rather than other sources of carbohydrate to treat hypoglycemia.

During the outpatient phase the subject will be provided with the following items for recording study data and will be provided with instructions for use and uploading data to the cloud if applicable.

1. Blood Glucose Meter: Bayer[®] Contour Next One
 - a. Used to collect blood glucose values during exercise sessions and to confirm blood glucose if a value ≤ 70 mg/dL (3.89 mmol/L) is indicated by CGM.
2. Dexcom[®] G5 Continuous Glucose Meter
 - a. Used to collect interstitial glucose measurements on a continuous basis.
3. Fitbit[®] Ionic
 - a. Use to collect exercise session metrics (heart rate) and daily activity metrics
 - b. Subjects will maintain a food log in the Fitbit application
4. Paper Diary
 - a. Description of exercise type, start/stop time of exercise
 - b. Glucose tab usage and emergency kit usage
 - c. Time and volume of administration of Study Medication

10.4.2. Visit 11 – Follow-Up Visit (14-21 Days After Last Exercise Session)/Early Termination

Subjects will be asked to return the clinic 14 - 21 days from the last exercise session for the following evaluations. The subject will be asked to return to the clinic for this same list of evaluations upon early termination from the study.

1. Concomitant medication changes.
2. Focused PE, including measurement of height and weight (no shoes, lightly clothed), but excluding genital/pelvic exams.
3. 12-lead ECG after subject has completed a minimum of 5-minute supine rest.
4. Vital signs measurements, including measurements of temperature, respiration rate, heart rate, and BP, after a 5-minute seated rest.
5. Urine pregnancy test for women of childbearing potential.
6. Collection of venous blood for complete blood count (without differential) and serum chemistry.

A fasting blood sample (minimum 8 hours) will be taken for measurement of HbA1c.

7. AE assessment.
8. Questionnaires/Forms will be filled out: Barriers to Physical Activity Diabetes (Type 1) (BAPAD-1), Hypoglycemia Fear Survey (HFS) and Hypoglycemia Confidence Scale (HCS).

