Objectives	
Primary Objective:
 
To evaluate if the subcutaneous (SC) administration of Glucagon RTU (Glucagon Injection) just before exercise, with or without a 50% reduction in basal rate insulin, compared to a 50% basal rate insulin reduction alone, prevents the occurrence of hypoglycemia (ie, blood glucose \leq70 mg/dL; 3.89 mmol/L) measured by blood glucose meter (BGM) during and after

	moderate-to-high intensity aerobic exercise by adult subjects with T1D in an outpatient setting.
	
Secondary Objectives:
 
 1. To evaluate how Glucagon RTU (Glucagon Injection) contributes to prevention of hypoglycemia during exercise and post-exercise recovery. 2. To evaluate the effect of Glucagon RTU (Glucagon Injection) on insulin utilization during 12 weeks of out-patient exercise. 3. To evaluate the effect of Glucagon RTU (Glucagon Injection) on patient-reported outcomes (PROs) of: Barriers to Physical Activity Diabetes (Type 1) (BAPAD-1), Hypoglycemia Fear Survey (HFS) and Hypoglycemia Confidence Scale (HCS) after 12 weeks of outpatient exercise.
Endpoints	
Primary Endpoint: Incidence of hypoglycemia (ie, blood glucose \leq70 mg/dL; 3.89 mmol/L) associated with an exercise session across 12 weeks of outpatient treatment as measured by blood glucose measurements (BGM).
 
Key Secondary Endpoints:
 
 1. Glucose levels below target range, measured by unblinded CGM (inpatient and outpatient), defined as both time (in minutes) and mean decremental area over the curve (AUC(0-300 min) in minutes*mg/dL) during exercise: 
 • Below range, as defined by interstitial glucose (IG) \leq 70 mg/dL (3.89 mmol/L) • Below range, as defined by IG between 54 to - 70 mg/dL (3 – 3.89 mmol/L) • Below range, as defined by IG $<$ 54 mg/dL (3 mmol/L) • Proportional time (percentage time within hypoglycemia IG \leq 70 mg/dL (3.89 mmol/L) and clinically significant hypoglycemia IG $<$ 54 mg/dL (3 mmol/L)) 2. Change from Baseline at the end of the Outpatient Phase in the following PROs: Barriers to Physical Activity in Diabetes (Type 1) (BAPAD-1), Hypoglycemia Fear Survey (HFS-II), Hypoglycemic Confidence Scale (HCS). 
Other Secondary Endpoints
 
 • Change from Baseline at Weeks 4, 8, and 12 in insulin utilization as reported by the subject in the Outpatient Phase.

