5.1.2. Secondary Objectives

- To evaluate how Glucagon RTU (Glucagon Injection) contributes to prevention of hypoglycemia during exercise and post- exercise recovery
- To evaluate the effect of Glucagon RTU (Glucagon Injection) on insulin utilization during exercise.
- To evaluate the effect of Glucagon RTU (Glucagon Injection) on PROs BAPAD-1, HFS-II, and HCS after 12 weeks of outpatient exercise

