5.2.2. Key Secondary Endpoints

- Glucose levels below target range, measured by unblinded CGM (inpatient and outpatient), defined as both time (in minutes) and mean decremental area over the curve (AUC(0-300 min) in minutes*mg/dL) during exercise:
 - • Below range, as defined by interstitial glucose (IG) \leq 70 mg/dL (\leq 3.89 mmol/L)
 - • Below range, as defined by IG between 54 to 70 mg/dL (3 – 3.89 mmol/L)
 - • Below range, as defined by IG $<$ 54 mg/dL ($<$ 3 mmol/L)
 - • Proportional time (percentage time within hypoglycemia IG \leq 70 mg/dL (3.89 mmol/L) and clinically significant hypoglycemia IG $<$ 54 mg/dL (3 3 mmol/L))
- Insulin utilization as reported by the subject at Baseline, Weeks 4, 8, and 12 in the Outpatient Phase.
- Change from Baseline to the end of the Outpatient Phase in PROs: Barriers to Physical Activity in Diabetes (Type 1) (BAPAD-1), Hypoglycemia Fear Survey (HFS-II), and Hypoglycemic Confidence Scale (HCS),

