9.1.4. Barriers to Physical Activity Diabetes (Type 1) Questionnaire

The Barriers to Physical Activity in Diabetes (Type 1) (BAPAD-1) is a 12-question instrument to assess the likelihood that a subject with T1D will exercise within the next 6 months; it is completed by the subject for the first time at Visit 3 and is also completed at the Follow-up Visit. Subjects are asked the question: “Indicate the likelihood that each of these items would keep you from practicing regular physical activity during the next 6 months?” and they are to respond by rating the 12 responses with a “1” (unlikely) to “7” (extremely likely). The higher the score, the less likely the subject is to engage in exercise.

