9.1.5. Hypoglycemia Fear Survey II

The Hypoglycemia Fear Survey II (HFS-II) is a 33-item questionnaire, with 15 questions addressing actions the subject may take to avoid low blood glucose, and the remaining questions addressing fears the subject may have about low blood glucose. Responses range from a score of 0 (never) to 4 (almost always). The higher the score, the greater the subject’s fear of hypoglycemia. The HFS-II is completed at Visit 3 and the Follow-up Visit.

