9.1.6. Hypoglycemia Confidence Scale

The Hypoglycemia Confidence Scale (HCS) is a 9-item questionnaire that assesses the subject’s confidence about safety regarding hypoglycemia. The questionnaire has 4 responses possible for

each question, ranging from “not confident at all” to “very confident. The HCS is completed at Visit 3 and the Follow-up Visit.

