12.4.3. Analysis of the Key Secondary Endpoint(s)

Glucose levels will be measured and analyzed as the mean decremental area over the curve (AUC(0-5hrs) in minutes*mg/dL) during exercise. Analysis will be conducted for glucose levels below range (interstitial glucose \leq 70 mg/dL (3.89 mmol/L), interstitial glucose between 54-70 mg/dL (3 - 3.89 mmol/L), <54 mg/dL (3 mmol/L)) and proportional time (percentage within serious hypoglycemia <54 mg/dL (3 mmol/L)). Differences between treatment groups in daily glucose requirements with exercise and adherence to IP with exercise will be made using t- tests (not corrected for multiple comparisons). Change from baseline to end of study in BAPAD- 1, HFS-II and HCS will be conducted. Changes from baseline in PROs may be correlated with clinical measurements during the study.

Secondary endpoints will be analyzed using the ITT and PP populations. Glucose levels will be measured and analyzed as the mean decremental area over the curve (AUC(0-5hrs) in minutes*mg/dL) during exercise. Analysis will be conducted for glucose levels below range (interstitial glucose \leq 70 mg/dL (3.89 mmol/L), interstitial glucose between 54-70 mg/dL (3 - 3.89 mmol/L), <54 mg/dL (3 mmol/L)) and proportional time (percentage within serious hypoglycemia <54 mg/dL (3 mmol/L)). Differences between treatment groups in daily glucose requirements with exercise and adherence to IP with exercise to determine if subjects use fewer glucose tabs will be made using t-tests (not corrected for multiple comparisons). Change from baseline to end of study in BAPAD-1, HFS-II and HCS will be conducted. Changes from baseline in PROs may be correlated with clinical measurements during the study.

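### The patient-reported endpoint is set at the end of the Outpatient Phase, but after baseline the questionnaires are scheduled only at Visit 11/ET, which for completers is 14-21 days after the last session

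*Protocol*

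**What the plan says.** **Endpoint.** The protocol synopsis (2.1) gives "Change from Baseline at the end of the Outpatient Phase in the following PROs" and section 5.2.2 gives "Change from Baseline to the end of the Outpatient Phase in PROs". SAP section 3 repeats the 5.2.2 wording. The matching objective in Protocol 5.1.2 is the effect "after 12 weeks of outpatient exercise".

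**When the questionnaires are given.**
- BAPAD-1 (Protocol 9.1.4): "it is completed by the subject for the first time at Visit 3 and is also completed at the Follow-up Visit".
- HFS-II (9.1.5): "The HFS-II is completed at Visit 3 and the Follow-up Visit".
- HCS (9.1.6): "The HCS is completed at Visit 3 and the Follow-up Visit".
- The schedules of activities in both documents agree. Each questionnaire is marked at Visit 3 and at Visit 11 Follow-up/ET, and the column for Visits 5 to 10 is empty.

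**When Visit 11 takes place.** Protocol 10.4.2 says "Subjects will be asked to return the clinic 14 - 21 days from the last exercise session". Section 9.3.1.4 places the same visit 14-21 days after the last dose. Footnote f of the schedule, in both documents, says 14 days. Under 10.4.2, subjects who terminate early have the same evaluations at termination, and no waiting interval is given for them.

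**Analysis.** Protocol 12.4.3 plans "Change from baseline to end of study in" the three instruments. SAP 4.3.7 names the tests and an ANCOVA but no visit.

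**The concern.** The endpoint names one time point and the schedule supplies another. For completers, the only post-baseline answers come after two to three weeks without study drug. The table titles in SAP 5.1 nevertheless place the questionnaire results in the Outpatient Phase, so a reader of the tables would take them as end-of-treatment findings.

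The intervention is taken just before exercise, and two of the questionnaires ask about the subject's present or future state. A finding of no difference at Visit 11 could mean that there was no effect, or that there was one and it had faded; the data could not tell these apart. A difference would be reported for a time at which nobody was asked.

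Timing also varies between subjects, because early terminators answer on a different clock. If early termination differs by arm, the timing of the measurement differs by arm too.

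**Working it through.** **1. Timeline.** The synopsis gives 4 weeks of screening, 2 of CRC, 12 outpatient and 2 for the End of Study Visit: 4 + 2 + 12 + 2 = 20 weeks, which reproduces the stated participant duration. The End of Study Visit period is counted separately from the Outpatient Phase. The schedule's last outpatient day also reproduces: the latest Visit 4 is Day 29, and 29 + 84 = Day 113.

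**2. When completers answer.** Assume that the last session falls at the end of week 12.

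| Visit 4 on | Outpatient Phase ends | Visit 11 (+14 to +21 days) |
|---|---|---|
| Day 3 | 3 + 84 = Day 87 | Day 101 to 108 |
| Day 29 | 29 + 84 = Day 113 | Day 127 to 134 |

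Counted from the start of the Outpatient Phase, that is (84 + 14)/7 = week 14 to (84 + 21)/7 = week 15. An earlier last session would move the calendar day but not the 14-21 day lag.

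**3. Who answers on a different clock.** The sample-size section allows for 15% attrition among 48 subjects: 0.15 × 48 = 7.2. If attrition is as planned and each such subject attends the ET visit, about 7 values come without the 14-21 day lag.

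**4. What each instrument asks about.**
- HCS (Protocol Appendix 5) has no stated recall window and asks how confident the subject is. At Visit 11 that is confidence after 2-3 weeks off drug.
- BAPAD-1 (Appendix 2) asks about the coming 6 months, so it too is answered from the off-drug position.
- HFS-II (Appendix 3) looks back 6 months. Taking that as 182 days, the start of the Outpatient Phase is at most 84 + 21 = 105 days before Visit 11, so all 84 outpatient days are inside the window. They would also all be inside it at week 12. The off-drug stretch is 14/182 = 8% to 21/182 = 12% of the window, so the lag changes little for this instrument.

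**5. Is there a rule that closes the gap?**
- The SAP Introduction gives the SAP precedence over the protocol, and SAP section 3 keeps the end-of-phase definition.
- In the same section, exploratory endpoint 10 (body weight, for which the schedule marks Visit 11 as the only post-screening measurement) is defined to the end of the study. The SAP thus uses the two terms separately.
- SAP 2.4 defines the outpatient baseline but gives no window for the post-baseline value.
- SAP 2.2 rules out imputation, and SAP 4.4 lists no changes from the protocol.

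**6. Is there a week-12 visit?** Visits 5 to 10 are six visits two weeks apart. If Visit 5 is at week 2, Visit 10 is at week 2 + 10 = 12. If Visit 5 is at week 0, Visit 10 is at week 10. The documents do not say which. The week 4, 8 and 12 insulin time points make week 12 plausible. On either reading no questionnaire is scheduled at Visit 10.

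**The case against.** The best defence is that a post-baseline value is collected and that Protocol 12.4.3 names a time point that fits Visit 11. Visit 11 also comes, literally, after the 12 weeks named in the objective. The lag is the same for completers in all three arms, so no between-arm bias is shown among them. The documents contain no evidence that any effect fades within two to three weeks. This is a secondary endpoint in a 48-subject Phase 2 study of preliminary efficacy.

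Much of this stands. A reader might infer that the endpoint is never measured. That goes too far: it is measured late for completers, and at termination for those who leave early. A reader might also infer that the effect will be diluted by some definite amount, or that the trial is underpowered for these scales. The documents support neither: they state no rate of fading and no power or sample size for the questionnaires. The 14 per group comes from the primary endpoint alone.

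The defence does not remove the contradiction. The wording in 12.4.3 conflicts with an endpoint definition that the SAP keeps and that takes precedence, so it is one more passage to reconcile. Equal lag among completers does not settle how ET values are to be combined with theirs.

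**Conclusion.** The point holds as a mismatch between the endpoint's stated time and its schedule. No completer has a questionnaire scheduled at the end of the Outpatient Phase; the one post-baseline value comes 14-21 days later (or 14 days, by footnote f), after the last dose. Early terminators supply values with no stated lag, and no rule in the SAP covers either case. The consequence is a mislabelled endpoint with mixed timing. It matters most for HCS and BAPAD-1 and is small for HFS-II.

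The week 14-15 placement assumes a last session at the end of week 12. The figure of about 7 early terminators assumes attrition as planned and attendance at the ET visit. Whether answers change over the lag is unknown, so the direction and size of any distortion cannot be stated. No sample size, power or alpha figure changes. It should be corrected because the endpoint is a key secondary one and the correction is cheap.

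**What to change.** 1. Amend the protocol to give BAPAD-1, HFS-II and HCS at the end-of-week-12 outpatient visit, and use that value for the endpoint. This is Visit 10 if Visit 5 is at week 2; the amendment should say so explicitly. Keep Visit 11 as a separate follow-up value.
2. For subjects already past that visit, or if no amendment is feasible, relabel the endpoint in both documents and in the table titles as change to Visit 11, 14-21 days after last treatment.
3. In either case, state in the SAP whether and how ET values enter the analysis.
4. Reconcile the end-of-study wording in Protocol 12.4.3 with the endpoint definition, and footnote f's 14 days with the 14-21 days in Protocol 10.4.2.

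The cost of step 1 is an amendment and 12 + 33 + 9 = 54 more items at an existing clinic visit. Steps 2 to 4 are text edits.

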11. STUDY INTERVENTION DISCONTINUATION AND PARTICIPANT DISCONTINUATION/WITHDRAWAL

11.1. Discontinuation of Study Intervention

The Sponsor has the right to terminate the study at any time. In case of an early termination of the study for safety reasons, or temporary halt by the Sponsor, the REB should be notified by the Investigator within 15 calendar days and should be provided with a detailed written explanation for the termination/halt.

An end-of-study declaration will be submitted to the regulatory authorities and REB after study termination (once all subjects have completed their last follow-up visit). To allow close-out procedures, this notification should be submitted within 90 days after the end of the study.

11.2. Participant Discontinuation/Withdrawal from the Study

Subjects have the right to withdraw from the study at any time for any reason, including personal reasons. A subject can withdraw without giving a reason. The Principal Investigator should however try to find out why a subject withdraws from the study and document the reason for withdrawal in the source documents and on the electronic Case Report Form (eCRF).

Subjects may be withdrawn from the study in the event of:

- A severe AE or serious AE (SAE);
- Failure of the subject to comply with the protocol requirements or to cooperate with the Principal Investigator.

Subjects must be withdrawn from the study in the event of:

- Withdrawal of consent;
- Difficulties in obtaining blood or other samples;
- For safety reasons, in the Investigator's opinion, it is in the best interest of the subject that he/she be withdrawn;
- A positive pregnancy test (or if the subject is non-compliant with the contraception requirements);
- Development of a medical condition that requires concomitant treatment with a prohibited therapy.

The monitor and Sponsor should be informed: in case of subject withdrawal due to an SAE (for details on AE reporting), and the Sponsor should be notified within 24 hours. In case of withdrawal for other reasons; the Sponsor should be notified within 2 days from the event.

Subjects who are withdrawn from the study prior to completion of the scheduled study procedures for any reason (AE, withdrawal of consent, etc.) should be invited to complete the assessments as indicated in the Schedule of Activities, Early Termination Visit ([Table 1](#)). In case of an AE, the appropriate follow-up will be conducted.

12. STATISTICAL CONSIDERATIONS

12.1. General Approach

Descriptive statistical methods will be used to summarize the data from this study, with hypothesis testing performed for the primary and other selected key efficacy endpoints. Unless stated otherwise, the term “descriptive statistics” refers to number of subjects (n), mean, median, SD, minimum, and maximum for continuous data and frequencies and percentages for categorical data. Subject disposition will be presented for all subjects for each stage (CRC and Outpatient). The number of subjects who completed the study and discontinued from the study will be provided. The reasons for early discontinuation also will be presented.

Analyses will be performed for data collected during the CRC visits separately from the data collected during the parallel designed outpatient part of the study. A stand-alone Statistical Analysis Plan (SAP) will be developed to include complete details for all planned analyses.

12.2. Sample Size Determination

The primary endpoint of the study is the incidence of hypoglycemia (glucose \leq 70 mg/dL (3.89 mmol/L)) associated with an exercise session, which occurred within the 12 weeks outpatient follow-up, as measured by BGM. The null hypothesis is that there is no difference between the treatment groups in the mean incidence of exercise associated hypoglycemia, and the alternative is there is a difference between the treatment groups in terms of the mean incidence of exercise associated hypoglycemia. With an effect size estimate of 0.262 (variance of means 59, common standard deviation 15), 80% power and an alpha of 0.05, using a one way analysis of variance, 14 subjects per treatment group in the Outpatient Stage is required.

Accounting for 15% attrition, a total of 48 subjects will be randomized.

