8.5. Measures to Minimize Bias: Randomization and Blinding

The study statistician will create the randomization schedule for the study. The randomization assignment for the participant will be conducted once at the time of enrollment with confirmation of subject eligibility. The CRC assignments will be by random assignment during the first session to either Glucagon RTU or placebo. At the second session, the participant will be crossed over to the other treatment assignment. At the completion of the CRC visits, the subject

will then have the treatment assignment applied for the parallel group study. The randomization schedule methodology for the Outpatient setting is by permuted random block to 1 of 3 treatment assignments in a 1:1:1 ratio.

1. A 50% reduction in basal insulin rate 5 minutes before exercise + pre-exercise injection of placebo (blinded)
2. A 50% reduction in basal insulin rate 5 minutes before exercise + pre-exercise injection of Glucagon RTU (blinded)
3. No reduction in basal insulin rate + pre-exercise injection of Glucagon RTU (open label)

The cross-over study is blinded to the extent possible since all participants will receive both Glucagon RTU and placebo. All staff, participants and study team members will know that the participant will receive both study treatments during the CRC sessions. During the outpatient study, two of the treatments will be blinded to the study staff, participants and Sponsor. One arm of the study will be open-label. It is imperative for the study staff to remain blinded to treatment assignment prior to randomization and during the study treatment periods as not to bias the outcome.

Glucagon RTU and placebo will be prepared and administered so that each will be indistinguishable from the other.

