12.4.2. Analysis of the Primary Efficacy Endpoint(s)

The primary efficacy analysis will be analyzed by ANOVA comparing the mean incidence rate among the 3 treatment groups. All statistical significance testing will be 2-sided with a p-value <0.05 . Efficacy endpoints will be analyzed using the ITT and PP analysis populations. After performing the F-test and if an overall $p<0.05$ is achieved, post-hoc analysis of group means will be conducted to statistically determine which group means differ.

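### A 15% loss from 48 randomized leaves 13.6 per arm rather than the required 14; 48 covers a 12.5% loss, and the effect on power is small

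*Protocol*

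**What the plan says.** Protocol 12.2 sizes the Outpatient Stage on a one-way ANOVA of the per-subject incidence of exercise-associated hypoglycemia across three arms. The inputs are "With an effect size estimate of 0.262 (variance of means 59, common standard deviation 15"), with "80% power and an alpha of 0.05". The result is that "14 subjects per treatment group in the Outpatient Stage is required". The attrition sentence follows directly: "Accounting for 15% attrition, a total of 48 subjects will be randomized". SAP 1.3 repeats the inputs, the requirement and the attrition sentence.

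Protocol 8.5 allocates the outpatient treatments by "permuted random block to 1 of 3 treatment assignments in a 1:1:1 ratio", so 48 means 16 per arm. Neither document gives the formula used to allow for attrition, says how many subjects are expected to remain, or defines whether attrition means leaving the study or having no analysable data.

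**The concern.** A reader takes the attrition sentence to mean that, after 15% are lost, the required 14 per group will still be there. Multiplying 48 by 0.85 shows that they will not. The SAP states that it takes precedence over the protocol and lists no changes from it, so the mismatch also stands in the controlling document, and no other section resolves it.

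What is at stake is the accuracy of a stated design figure. The allowance has some work to do. Subjects are randomized once, at Visit 3, before either CRC session, whereas the 14 per group are needed in the later Outpatient Stage, so CRC-phase losses also count against it. SAP 2.2 rules out imputation, so a subject with no usable outpatient session supplies no incidence rate.

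**Working it through.** **Inputs.** From Protocol 12.2: variance of means 59, common SD 15, alpha 0.05, power 80%, 14 per group, 15% attrition, 48 randomized. From Protocol 8.5: three arms, 1:1:1.

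**Step 1: reproduce the 14 per group.** The stated effect size is 59/15² = 59/225 = 0.262, which is f² (f = 0.512). For three arms with N analysable subjects in total, the F-test has 2 and N − 3 degrees of freedom and noncentrality λ = N × 59/225. Power is the probability that this noncentral F exceeds the 5% critical value of the central F.

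| Per arm | N | λ | Power |
|---|---|---|---|
| 13 | 39 | 10.23 | 0.789 |
| 14 | 42 | 11.01 | 0.823 |

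Fourteen is the smallest whole number per arm that reaches 80%, so the plan's figure reproduces exactly. Rounding up leaves a little slack (82.3% against 80%).

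**Step 2: apply the stated attrition to 48.**
- Required: 3 × 14 = 42.
- Expected to remain: 48 × (1 − 0.15) = 40.8, or 16 × 0.85 = 13.6 per arm.
- Expected shortfall: 42 − 40.8 = 1.2 subjects.

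**Step 3: find the attrition that 48 does cover.** (48 − 42)/48 = 6/48 = 12.5%, or 2 of 16 in each arm. Keeping 14 in every arm also requires the losses to be spread evenly.

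**Step 4: find the number that covers 15%.** 42/0.85 = 49.4, so 50 in total. For equal arms, 14/0.85 = 16.5, so 17 per arm and 51 in total (check: 17 × 0.85 = 14.45).

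**Step 5: a possible origin of 48.** 42 × 1.15 = 48.3, or 16.1 per arm, which rounds to 16 per arm and 48 in total. This would add 15% of the analysable number instead of allowing for 15% of those randomized. It is an inference, since the documents give no formula, and the mismatch in Step 2 does not depend on it.

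**Step 6: power near the expected number.** Using λ = N × 59/225 as in Step 1:

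| N | Power (equal-arm approximation) |
|---|---|
| 42 | 0.823 |
| 41 | 0.812 |
| 40 | 0.801 |
| 39 | 0.789 |

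The formula is exact only for equal arms, and neither 41 nor 40 divides by three. The plan gives a variance of means but not the means, so two patterns with variance 59 and SD 15 were assumed: one arm different from the other two, and three equally spaced means. Placing the short or long arm in each position gives:

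| Arm sizes | N | Power range |
|---|---|---|
| 14/14/13 | 41 | 0.802 to 0.822 |
| 14/13/13 | 40 | 0.791 to 0.811 |
| 14/14/12 | 40 | 0.777 to 0.821 |

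**Step 7: chance variation in losses.** If each of the 48 has an independent 15% chance of being lost (an assumption, not a statement in the plan), the probability of losing more than 6, and so falling below 42, is about 59%. The probability of losing 9 or more, leaving 39 or fewer, is about 29%.

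**The case against.** The best defence has three parts.

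*The text promises less than a reader may assume.* It says that attrition is accounted for. It does not say how, or that 14 per group will remain after a 15% loss. Adding 15% to 42 is a crude convention, but it gives a round 16 per arm and falls only 49.4 − 48 = 1.4 subjects short of the division method. This stands as a reason to treat the point as small. It does not reconcile the figures: the sentence follows directly on the requirement of 14, and an allowance for attrition has no evident purpose except to protect that number.

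*Not everyone who leaves is lost to the analysis.* The ITT population is all randomized subjects. The per-protocol population asks for a qualified exercise session, not completion of 12 weeks. The endpoint is a rate per subject over the sessions performed. Someone who leaves in week 8 can therefore still supply a value, though a less precise one. This stands, and it means the loss of analysable subjects may be below 15%. It does not help for subjects with no usable outpatient session, such as those who leave during the CRC phase. The documents also do not say whether the 15% already refers to subjects without analysable data.

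*Power is hardly affected.* This stands too. A reader might infer from the shortfall that the trial is underpowered at its planned attrition. The documents do not support that: because 14 was rounded up, the plan's own inputs still give about 80 to 81% at 40 to 41 subjects. Nor can it be said that 80% is guaranteed at 40, because the unequal-arm range runs on either side of it.

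**Conclusion.** The point holds as a correction to a stated figure. With 14 per group required and 48 randomized, the design covers a 12.5% loss, not 15%. At 15%, the expected number is 40.8 (13.6 per arm), about one subject short of 42. Power remains roughly 80%, within about 0.78 to 0.82 at 40 to 41 analysable subjects, so no design decision turns on it.

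This rests on the plan's variance of 59 and SD of 15, taken as given and not tested here for fit to the endpoint. It also rests on reading attrition as loss of analysable subjects; if partial dropouts contribute a rate, the gap shrinks further. The ranges for unequal arms depend on the two assumed patterns of means. Two stronger readings are not supported: that the trial falls materially below its target power, and that the documents themselves show which inflation rule was applied. The matter is minor, but the sentence should be put right.

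**What to change.** Keep 48 randomized. In Protocol 12.2 and SAP 1.3, replace the attrition sentence with wording such as: *48 randomized (16 per group) allows for 12.5% attrition while retaining 14 analysable subjects per group.* It would help to state in the same place that attrition here means having no analysable outpatient data, if that is what is intended.

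If the sponsor wants to quote power at 15% loss, give it as approximately 80% and label it an equal-arm approximation; a more precise figure would need assumed group means, which the plan does not provide. If instead the 15% allowance is to be kept as stated, the matching totals are 50, or 51 with equal arms.

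The recommended change costs one sentence in each document, with no extra patients and no change to the analysis.
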